6. STATISTICAL METHODS OF ANALYSIS

6.1 General Principles

The statistical analyses will be performed by Quartesian LLC, with approval of the Sponsor, using SAS Version 9.4 (or higher). All tables, figures and listings will be produced in landscape format.

In general, all data will be listed by subject and visit/time point where appropriate. The summary tables will be stratified by, or have columns corresponding to, treatment groups.

The total number of subjects in the treatment group (N) under the specified population will be displayed in the header of summary tables.

Data will be summarized using descriptive statistics for continuous variables. Unless otherwise specified, descriptive statistics will include number of subjects, mean, standard deviation, minimum, median and maximum. Number of subjects with missing values will also be displayed, but only if non-zero. The minimum and maximum statistics will be presented to the same number of decimal places as the original data. The mean and median will be presented to one more decimal place than the original data. The standard deviation will be presented to two more decimal places than the original data.

In summary tables of categorical variables, counts and percentages will be displayed. The count [n] indicates the actual number of subjects in a particular category, which should always be less

than or equal to the total number of subjects in the respective study group with known (non-missing) category [M]. Percentage will be obtained by: % = n/M*100. Unless otherwise specified, all percentages will be expressed to one decimal place.

All statistical tests will be two-sided at a significance level of $\alpha = 0.05$, unless otherwise indicated.

Baseline will be defined as the last assessment, scheduled or not, prior to the first dose of the study drug, unless otherwise specified.

In by-visit summaries, only data collected on scheduled visits/timepoints will be summarized. Data from unscheduled assessments will be included in listings and may be used in determination of baseline if applicable.

Relative days will be calculated relative to date of first dose of the study drug. Relative days will be calculated as follows only when the full assessment date is known (i.e., partial dates will have missing relative days).

For assessment on or after the day of first dose of the study drug:

Relative Day = Date of Assessment – Date of First Dose of Study Drug+1.

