6.1.1 Treatment Groups

Findings collected up to Week 24 visit will be analyzed by treatment groups based on the treatments that subjects take in Part I of the study:

- Placebo
- AS012
- AS012
- AS012
- AS012

Findings collected after Week 24 visit (including those in the follow-up part of the study) will be analyzed by treatment groups based on the treatments that subjects take in Part II of the study:

- Placebo/AS012
- Placebo/AS012
- AS012
- AS012
- AS012
- AS012

Note that subjects initially randomized to Placebo and re-randomized to AS012 doses after Week 24 will not be pooled with subjects taking the same doses from the study start due to different exposure times.

Adverse events will be analyzed by actual treatment at the time of event onset, i.e., using the same treatment groups as findings collected up to Week 24.

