6.9.2.4 Time to re-pigmentation

Times to re-pigmentation of 10%, 25%, 75%, 90% and 100% are defined as the time from the first dose of the study drug to the first assessment where VASI 10, VASI 25, VASI 75, VASI 90 and VASI 100 correspondingly are achieved. The time will be measured in weeks. For subjects who never achieved the corresponding VASI reduction, the time will be censored at the last VASI assessment.

For subjects who are initially randomized to placebo time to re-pigmentation will be defined separately for the Placebo treatment during Part I of the study and AS012 treatment during Part II of the study. For Placebo treatment the time to re-pigmentation will start with the first placebo dose and will be censored at the last VASI assessment while on placebo. For AS012 treatment the time will start with the first AS012 dose and will be censored at the last assessment after the switch to AS012.

Quartiles of time to re-pigmentation over the 52 weeks of treatment with their 95% confidence intervals will be calculated by treatment group.

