6.11.1 Adverse Events

Adverse Events will be coded using the MedDRA (Version 23.1) AE coding system for purposes of summarization.

[figure not shown]
An AE will be considered as treatment-emergent (TEAE) if the date of onset is on or after the date of the first study drug administration. AEs with unknown start dates will be counted as treatment-emergent unless the AE resolution date is prior to the study drug start date. If the start date is partially missing, the AE will be considered treatment-emergent, unless the month and year (when available) rule out the possibility that the event occurred post start of study drug dosing.

A TEAE is defined as treatment-related if its relationship to study medication is recorded as "Possible", "Probable" or "Definite" on the eCRF. In case the relatedness was not assessed, the most conservative result (related) will be chosen for the analysis.

For subjects initially randomized to Placebo and later re-randomized to AS012 AEs will be assigned to either Placebo or AS012 treatment based on the date of onset, i.e., AEs that start prior to the first dose of AS012 will be assigned to the Placebo treatment and AEs that start on or after the date of the first AS012 dose will be assigned to the AS012 treatment.

TEAEs will be defined as occurring in Part I of the study if the date of onset is prior to the date of the subject's Week 24 visit. For subjects who discontinue prior to Week 24 visits, all their TEAEs will be defined as occurring in Part I. AEs starting on or after the date of the subject's Week 24 visit will be defined as occurring after Part I.

All summaries of TEAEs will be presented in three ways:

In summaries of TEAEs a subject experiencing the same AE multiple times on the same treatment will only be counted once for that preferred term and treatment. Similarly, if a subject experiences multiple AEs within the same system organ class on the same treatment that subject will be counted only once in that system organ class and treatment. When summarizing AEs by severity, only the most severe occurrence within the preferred term or system organ class and treatment will be used. Similarly, when summarizing AEs by

relationship to study drug, only the most related occurrence within the preferred term or system organ class and treatment will be selected for displays in summary tables.

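### SAP 6.9.2.4 restarts the placebo switchers' re-pigmentation clock at the first AS012 dose, but no visible text resets the VASI baseline, so improvement on placebo can count as AS012 response

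*SAP*

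**What the plan says.** SAP 6.9.2.4 measures time from the first dose of study drug to "the first assessment where VASI 10, VASI 25, VASI 75, VASI 90 and VASI 100 correspondingly are achieved". For those who begin on placebo and later switch, "time to re-pigmentation will be defined separately for the Placebo treatment during Part I of the study and AS012 treatment during Part II". The two periods have separate clocks. "For Placebo treatment the time to re-pigmentation will start with the first placebo dose", and censoring is at the final VASI on placebo. "For AS012 treatment the time will start with the first AS012 dose", and censoring is at the final assessment following the switch. Quartiles with 95% confidence intervals are then reported by treatment group for the 52-week treatment period.

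The section gives no reference value for the percentage reduction in the AS012 period. The general rule is in SAP 6.1: "Baseline will be defined as the last assessment, scheduled or not, prior to the first dose of the study drug, unless otherwise specified".

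SAP 6.1.1 reports switchers in their own Placebo/AS012 groups. They "will not be pooled with subjects taking the same doses from the study start due to different exposure times".

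**The concern.** The clock and the censoring are reset at the switch. As far as the visible text shows, the value from which improvement is measured is not. An AS012 time built this way pairs change since Day 1 with time since Week 24.

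A subject who had already improved enough on placebo, and simply stays there, is then an AS012 event at the first VASI after the switch. The same improvement may already have been counted as an event in the placebo summary. No visible rule removes or flags such subjects.

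At stake is how the switcher columns are read. They are the only data on what happens when a placebo subject starts AS012, and a short median there would naturally be taken as onset of effect. Under this rule it could appear with no drug effect at all.

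**Working it through.** **Which baseline applies.** The 6.1 rule turns on whether placebo counts as study drug. Three places in the SAP indicate that it does:
- 6.9.2.4 starts the general clock at the first dose of study drug and starts the placebo clock at the first placebo dose. It needs a separate sentence to move the clock to AS012.
- 6.8 uses the study drug administration form for dosing at both Visit 2 and Visit 7.
- Where the SAP means the switch, it names AS012. In 6.11.1, for example, "AEs that start prior to the first dose of AS012 will be assigned to the Placebo treatment".

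So, unless hidden text says otherwise, a switcher's baseline is the pre-placebo value.

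**Illustration (assumed values).** Day 1 VASI is 20, Week 24 VASI on placebo is 17.5, and it does not change afterwards. Against Day 1 the reduction is (20 − 17.5)/20 = 12.5%, a VASI 10 event on AS012. Against Week 24 it is (17.5 − 17.5)/17.5 = 0%, no event.

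**Size at planning values.** The documents give no figure for this endpoint, so there is none to reproduce. Inputs from SAP 3.2 are mean baseline VASI 15.7, placebo improvement 1.56 (10% of 15.7 is 1.57, a rounding difference) and SD of change 6.4. Taking change as normal and baseline at its mean, the share of placebo subjects already past VASI x at Week 24 is

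1 − Φ((x/100 × 15.7 − 1.56)/6.4)

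- VASI 10: (1.57 − 1.56)/6.4 = 0.002, giving 49.9%
- VASI 25: (3.925 − 1.56)/6.4 = 0.370, giving 35.6%
- VASI 75: (11.775 − 1.56)/6.4 = 1.596, giving 5.5%
- VASI 90: (14.13 − 1.56)/6.4 = 1.964, giving 2.5%
- VASI 100: (15.7 − 1.56)/6.4 = 2.209, giving 1.4%

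With 52 evaluable placebo subjects re-randomized 1:1, each switch group has about 26. That is 0.499 × 26 ≈ 13 subjects carried over for VASI 10 and 0.356 × 26 ≈ 9 for VASI 25.

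**Sensitivity.** Baselines were simulated (normal and lognormal, mean 15.7, SD 8.9, restricted to VASI of at least 4). Change was modelled on the percentage scale and on the absolute scale. The two smaller SDs are assumptions.

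| SD of change | VASI 10 | VASI 25 | VASI 75 |
|---|---|---|---|
| 6.4 | 49% to 50% | 34% to 36% | 6% to 11% |
| 3.2 | 48% to 50% | 23% to 27% | 0% to 3% |
| 1.57 | 46% to 51% | 7% to 17% | 0% to 1% |

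The VASI 10 share is stable because the threshold equals the assumed mean placebo improvement. The VASI 25 share depends on the SD.

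**Inert drug after the switch.** If VASI stays at its Week 24 value, the Day 1 baseline gives about 50% VASI 10 events at the first post-switch assessment, and a Week 24 baseline gives 0%. Now add assumed visit-to-visit noise of SD 1 or 2 points. The mean Week 24 value is 15.7 − 1.56 = 14.14, so a 10% reduction is 1.414. The Week 24 baseline then gives 1 − Φ(1.414/1) = 8% or 1 − Φ(1.414/2) = 24%. The Day 1 baseline still gives about 50%.

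**The case against.** **The baseline is inferred.** 6.9.2.4 does not say that the Day 1 value is kept. That follows from a general rule with an explicit exception clause, and the likely places for an exception are not visible: SAP 4.3 shows no content, and the text between 6.9.1.2 and 6.9.2.3 is missing. The definitions of VASI 10 to 100 appear nowhere in the visible text. This stands. The supportable statement is that no visible text resets the baseline, not that the plan expressly keeps it.

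**The effect is uneven.** It is large for VASI 10, depends on the SD for VASI 25, and is small for VASI 75 to 100. The SAP itself calls the SD of 6.4 conservative, and a smaller SD lowers the VASI 25 share. This also stands.

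**The consequence is limited.** The visible text plans quartiles and confidence intervals only. SAP 6.1.2 draws no inference from p-values outside the primary endpoint, and switchers have their own columns. That limits the damage, but separate columns do not remove a bias that arises inside them.

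**A reader might infer that switchers would look faster than subjects on the same dose from Day 1.** The documents do not support this. The first visible post-baseline VASI is at Week 12 (Protocol 7.4). The first focused-area visit after the switch is Week 36 (Protocol 7.9, with its assessment list not visible). The shortest possible time may therefore be about 12 weeks in both groups. At the planned improvement of 5.50, Φ((5.50 − 1.57)/6.4) = 73% of AS012 subjects meet VASI 10 at Week 24. If half that improvement (2.75, an assumption) is reached by Week 12, Φ((2.75 − 1.57)/6.4) = 57% meet it then. Both medians could thus be the first interval.

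**Reduction from original disease extent is a legitimate quantity.** True, but it does not match a clock that starts at the switch.

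**Conclusion.** The concern holds for the switchers' AS012 times, with medium confidence. Followed as visibly written, the rule lets improvement on placebo count as AS012 events. With an inert drug, the median AS012 time to VASI 10 in the Placebo/AS012 groups could fall at or near the first post-switch assessment. The sizes rest on the SAP's planning mean and SD, a normal model for change, and Week 24 status persisting after the switch.

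The Week 24 primary analysis and the subjects on AS012 from Day 1 are not affected. If the hidden definitions already set a Part II baseline, what remains is a missing cross-reference in 6.9.2.4.

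**What to change.** In SAP 6.9.2.4, for subjects first randomized to placebo:

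- State that VASI 10 to 100 in the AS012 period are computed from the last VASI before the first AS012 dose, normally the Week 24 assessment. Exclude subjects with VASI 0 at that point, because a percentage reduction is undefined for them.
- State that events and censoring stop at Week 52. Protocol 7.13 schedules a VASI at the off-treatment Week 64 visit, which the present censoring rule could take in although the quartiles are meant for the 52-week treatment period.

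No new data are needed, since VASI is already taken at Visit 7 (Protocol 7.7). The cost is a short addition to the SAP, one derived variable, and slightly less favourable figures for switchers.

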6.11 Safety Analyses

All safety analyses will be performed on the Safety population.

6.11.1 Adverse Events

Adverse Events will be coded using the MedDRA (Version 23.1) AE coding system for purposes of summarization.

[figure not shown]
An AE will be considered as treatment-emergent (TEAE) if the date of onset is on or after the date of the first study drug administration. AEs with unknown start dates will be counted as treatment-emergent unless the AE resolution date is prior to the study drug start date. If the start date is partially missing, the AE will be considered treatment-emergent, unless the month and year (when available) rule out the possibility that the event occurred post start of study drug dosing.

A TEAE is defined as treatment-related if its relationship to study medication is recorded as "Possible", "Probable" or "Definite" on the eCRF. In case the relatedness was not assessed, the most conservative result (related) will be chosen for the analysis.

For subjects initially randomized to Placebo and later re-randomized to AS012 AEs will be assigned to either Placebo or AS012 treatment based on the date of onset, i.e., AEs that start prior to the first dose of AS012 will be assigned to the Placebo treatment and AEs that start on or after the date of the first AS012 dose will be assigned to the AS012 treatment.

TEAEs will be defined as occurring in Part I of the study if the date of onset is prior to the date of the subject's Week 24 visit. For subjects who discontinue prior to Week 24 visits, all their TEAEs will be defined as occurring in Part I. AEs starting on or after the date of the subject's Week 24 visit will be defined as occurring after Part I.

All summaries of TEAEs will be presented in three ways:

In summaries of TEAEs a subject experiencing the same AE multiple times on the same treatment will only be counted once for that preferred term and treatment. Similarly, if a subject experiences multiple AEs within the same system organ class on the same treatment that subject will be counted only once in that system organ class and treatment. When summarizing AEs by severity, only the most severe occurrence within the preferred term or system organ class and treatment will be used. Similarly, when summarizing AEs by

relationship to study drug, only the most related occurrence within the preferred term or system organ class and treatment will be selected for displays in summary tables.

An overall summary for the Safety population will include, by treatment and overall, the number and percentage of subjects reporting at least 1 TEAE in the following categories:

- Any TEAE
- Treatment-related TEAE
- Serious TEAE
- Treatment-related serious TEAE
- TEAE leading to discontinuation of the study medication
- Treatment-related TEAE leading to discontinuation of the study medication
- TEAE requiring temporary interruption of study medication
- Treatment-related TEAE requiring temporary interruption of study medication
- TEAE leading to death.

The following TEAE frequency tables will be prepared summarizing the overall number of TEAEs, the number and percentage of subjects reporting at least one TEAE by MedDRA System Organ Class (SOC) and preferred term (PT), by treatment group for the Safety population:

- All TEAEs
- Serious TEAEs
- Treatment-related TEAEs
- AEs leading to discontinuation of the study medication
- TEAEs by Severity
- TEAEs by Relationship to Study Drug.

Overall summary of TEAEs and the summary of TEAEs by SOC and PT will be presented separately for TEAEs occurring in Part I, occurring after Part I and for all TEAEs for subjects initially randomized to AS012 treatment.

All information pertaining to AEs noted during the study will be listed by subject, detailing verbatim, preferred term, system organ class, start date, stop date, intensity, outcome, action taken and causal relationship to the study drug. The AE onset will also be shown relative (in number of days) to the date of first administration of the study drug. In addition the AE duration (if AE Stop Date is available) will be evaluated as below and presented (in number of days).

AE Duration = AE Stop Date - AE Start Date + 1

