## 5.7 Adverse Events (AEs)

Any AEs reported after signing Informed Consent should be reported. An adverse event is defined as any untoward medical occurrence (sign, symptom or abnormal laboratory finding) regardless of severity in a Subject or clinical-trial Subject administered a medicinal product and which does not necessarily have to have a causal relationship with this treatment. All adverse events, whether observed by an Investigator or Study Coordinator or reported by the Subject, whether related to study drug or not related to study drug, shall be documented on Subject records, together with details, i.e. date of onset, description of the AE, the duration and intensity of each episode, the action taken, the relationship to the investigational product and the degree of severity, the seriousness, date of resolution, and the outcome.

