### 9.7 Safety Assessment

Safety Assessments will include vital signs, physical examination, adverse events (AEs), laboratory tests, ECG monitoring, chest X-ray (if not done in last 6 months) and Columbia-Suicide Severity Rating Scale (C-SSRS).

The safety of AS012 will be evaluated by:

- o Incidence, seriousness and severity of all adverse events
- Shifts from baseline in hematology and laboratory tests
- Change from baseline in ECG parameters; Frequencies and percentages of ECG findings

The extent of exposure will be summarized using descriptive statistics. No inferential analyses are planned.

Incidence of all adverse events reported during the study will be summarized using the Medical Dictionary For Regulatory Activities (MedDRA) dictionary by System Organ Class and Preferred Term, by treatment group, severity, and relationship to study drug.

An AE is considered treatment emergent if it was not present prior to the first dose of treatment or, if it was present, it worsened in severity or treatment attribution.

Safety analyses will be performed on the Safety Population. All safety data will be listed by treatment and subject in data listings. AEs will also be summarized by actual dose at time of onset of the AE to account for possible dose reductions over the course of the study.

May 20, 2022 Protocol: **AS012-20-01** Page 50 of 88

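### SAP 6.11.1 defines treatment-emergent AEs by onset date alone and omits the protocol's clause for pre-existing events that worsen

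*SAP*

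**What the plan says.** Protocol 9.7 gives a definition with two limbs. An AE is treatment-emergent if it was absent before the first dose, "or, if it was present, it worsened in severity or treatment attribution".

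SAP 6.11.1 has one limb: the event counts "if the date of onset is on or after the date of the first study drug administration". Its rule for missing dates, "AEs with unknown start dates will be counted as treatment-emergent unless the AE resolution date is prior to the study drug start date", and its rule for partial dates are also date rules. Neither looks at severity or attribution.

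Collection starts before dosing. Protocol 5.7 states: "Any AEs reported after signing Informed Consent should be reported". Protocol 7.1 places screening in the 28 days before Day 1, with extension possible on approval, and AEs are assessed at both Screening and Baseline.

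Assignment to treatment is a separate rule. SAP 6.1.1 says "Adverse events will be analyzed by actual treatment at the time of event onset". For placebo subjects who move to AS012 after Week 24, SAP 6.11.1 says "AEs that start prior to the first dose of AS012 will be assigned to the Placebo treatment". Protocol 9.7 uses the same principle: "AEs will also be summarized by actual dose at time of onset of the AE".

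**The concern.** The SAP is meant to detail analyses that the protocol outlines. Here it narrows a safety definition, and the visible text gives no reason. The two definitions classify the same record differently.

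SAP 6.11.1 builds its overall summary and its tables by system organ class and preferred term on TEAEs: all, serious, treatment-related, leading to discontinuation, by severity and by relationship. An event that fails the TEAE test drops out of all of them, even if its worsening made it serious or led to stopping the study drug.

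Safety over 52 weeks is a secondary objective (SAP 2.2), and Protocol 9.7 plans no inferential safety analyses. The descriptive TEAE tables therefore carry most of the safety conclusion.

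**Working it through.** The plan states no figure to reproduce. The check sets the two definitions side by side and applies them to test records.

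**The definitions**

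- New after first dose: TEAE under both documents.
- Present before first dose and unchanged: TEAE under neither.
- Present before first dose and worse in severity or attribution afterwards: TEAE under Protocol 9.7, not under SAP 6.11.1 if the record keeps its onset date.

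**Test records**

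- *Case A.* The event starts between consent and first dose, worsens on study treatment and stays on one record with its first onset date. Protocol: TEAE. SAP: not a TEAE; it is absent from the TEAE tables and appears only in the by-subject listing. The result is the same in the placebo arm and in each AS012 arm.
- *Case B.* The event starts on placebo in Part I, worsens after the switch to AS012 and stays on one record. It is a TEAE under both definitions, because its onset follows the first dose of study treatment. The onset rule assigns it to placebo and to Part I. Subjects are counted once per preferred term and treatment, so the worsening adds nothing to placebo incidence. It does leave AS012 without an event. If the record holds the worst grade, the severity table shows that grade under placebo.
- *Case C.* The site records the worsening as a new event with its own onset date. SAP: TEAE under the treatment then being taken. Nothing is lost in either situation above.

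Case A is the contradiction between the documents. Case B comes from the assignment rule, not from the TEAE definition, and the protocol has the same rule. Its worsening clause refers to the first dose of treatment and is not restarted at the switch, so it does not resolve Case B either.

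**Size**

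The documents give no rate of screening-onset events and no rate of worsening. For illustration only, assume that 5% to 10% of subjects have an AE starting in screening and that 20% of these worsen on treatment without a new record:

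- 0.05 × 0.20 = 0.01, and 0.01 × 64 subjects per arm = 0.64
- 0.10 × 0.20 = 0.02, and 0.02 × 64 = 1.28

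That is about one subject per arm. All three rates are assumptions. If sites always open a new record, the number is zero.

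**The case against.** **Recording practice.** Sites may open a new record when an event worsens, which removes the problem. Protocol 5.7 and 10.1 ask for duration and intensity by episode, which points that way. But neither document defines an episode or says that worsening starts a new one with a new onset date. The objection limits the size of the effect; it does not remove the conflict.

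**Narrow exposure.** Only events that start before Day 1, persist and worsen are affected. They remain in the listings with dates, intensity, action taken and causality. Serious events are reported within 24 hours whatever their TEAE status (Protocol 10.3), and laboratory worsening appears in shift tables (SAP 6.11.2). All of this stands and supports a modest rating.

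**Caution elsewhere.** The SAP treats unknown start dates as treatment-emergent and missing relatedness as related. These rules are conservative, but neither reaches an event with a known onset before dosing.

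**Missing text.** Parts of the SAP are not visible, including the list of the three presentations of TEAE summaries. A declared departure from the protocol cannot be excluded.

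**Stronger readings.** A reader might infer that the SAP's definition charges worsening on AS012 to placebo and raises the placebo count. The documents do not support this: an event that began on placebo is already a placebo TEAE, and its assignment follows an onset rule that the protocol shares. A reader might also infer that the omission makes AS012 look safer. That is not shown, because the missing clause affects all five arms.

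**Conclusion.** The point holds for the TEAE definition: Protocol 9.7 and the visible SAP 6.11.1 disagree, and the SAP as written leaves out a class of events that the protocol counts. The certain effect is a lower absolute TEAE count in any arm where such events occur. A biased contrast with placebo would need worsening to be more frequent on drug. The size cannot be estimated from the documents and is probably small. The conclusion assumes that at least some worsenings stay on the existing record and that no unseen SAP text restores the clause.

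The Week 24 switch is a separate gap in both documents, not a contradiction. There, an AS012 worsening may go uncounted and a worse grade may be tabulated under placebo. The correction should be made because it is cheap and the TEAE tables are the main safety output.

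**What to change.** 1. Amend SAP 6.11.1 so that an AE is treatment-emergent if its onset is on or after the first dose, or if it was present before the first dose and worsened in severity or treatment attribution afterwards, as in Protocol 9.7. If the narrower definition is intended, state and justify the departure.
2. For the switch, add that an event ongoing at the first AS012 dose which later worsens is derived as an event dated at the worsening and assigned to the treatment then being taken. The earlier part stays under placebo with the severity it had there. State this openly as an addition to the onset rule in both documents.
3. Both rules need the date of worsening. If the eCRF does not capture it, tell sites to record a worsening as a new event with its own onset date.

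The cost is a short SAP amendment, one flag in the AE derivation and possibly a site instruction. AE counts may rise slightly.

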# 7.1 Visit 1: Screening Visit (Week ≥ -4 / Day -28 to -1)

Potential subjects will be screened during a 4-week period prior to randomization. CRO/Sponsor's approval is required on a case-by-case basis for an extension of the Screening Period to obtain all test results and to re-screen a subject. Re-screening is allowed once per subject; all assessments should be repeated using a new screening number. The new informed consent/assent is not required, unless an amended or revised informed consent/assent is introduced during the study.

The following procedures will be performed at Screening:

- 1. Written informed consent will be obtained. Subjects must have provided IRB approved written informed consent. Subjects will be given the approved ICF describing the study and any risks associated with participation. The Subject will be allowed as much time as needed to read and understand the information presented in the consent form. Appropriate study personnel will be available to answer any questions the Subject might have regarding the study or study-related procedures. If the Subject chooses to participate in the study, he or she will be asked to sign and date the consent form and will be provided with a copy for his or her records. The ICF must be signed by the Subject before any protocol assessments can be undertaken. Subjects participating the study, or those having skin biopsies taken, will be asked to sign a separate informed consent form in addition to the main study consent.
- 2. Demographics will be collected, including date of birth, gender, race and ethnicity.
- 3. A compliance with applicable inclusion and exclusion criteria will be reviewed. (See Sections 4.2, 4.3)
- 4. After confirming the eligibility, the Subject will be assigned a screening number.
- 5. A complete medical history will be obtained for the Subject's current and past medical conditions, including a complete list of current and past (within the previous 30 days) medications. Significant medical history should include, but not be limited to, evidence of hypertension, lipid disorders, obesity\*, heart attack, stroke, congestive heart failure, kidney disease, and auto immune disease and gestational diabetes. Significant surgical history should include, but not be limited to, removal of blockage from an artery and gallbladder removal. (See Section 5.1)
  - \* Obesity = BMI ≥30 (as defined by Metropolitan Life Insurance Company Chart)

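### The SAP's rule for partly missing AE onset dates omits the resolution-date check, so some AEs that ended before the first dose are counted as treatment-emergent

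*SAP*

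**What the plan says.** SAP 6.11.1 (Adverse Events) sets out three rules in succession.

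- Complete onset date: "An AE will be considered as treatment-emergent (TEAE) if the date of onset is on or after the date of the first study drug administration".
- No onset date: "AEs with unknown start dates will be counted as treatment-emergent unless the AE resolution date is prior to the study drug start date".
- Partly missing onset date: the event is treatment-emergent "unless the month and year (when available) rule out the possibility that the event occurred post start of study drug dosing".

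Protocol 9.7 (Safety Assessment) defines the same concept by presence before dosing: "An AE is considered treatment emergent if it was not present prior to the first dose of treatment or, if it was present, it worsened".

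Three further passages show that the situation can arise. Protocol 5.7 starts AE collection before dosing: "Any AEs reported after signing Informed Consent should be reported". Protocol 7.1 gives the length of the pre-dose window: "Potential subjects will be screened during a 4-week period prior to randomization". It can be extended case by case. SAP 6.11.1 also lists, for every AE, the "start date, stop date, intensity, outcome, action taken and causal relationship to the study drug", so the date needed to settle the matter is in the database.

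**The concern.** The resolution date appears in the rule for unknown onset and is absent from the rule for partial onset. Partial dates have their own sentence with a different exception, so a programmer who follows the text has no reason to carry the first exception over. The classification then stops being consistent: knowing the month or year of onset can turn a correct answer into a wrong one.

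At stake is the accuracy of the TEAE tables. An event that began and ended during screening cannot have been caused by study drug, and it cannot have worsened after dosing. If it enters the tables it adds noise to every arm, placebo included, and helps no comparison.

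**Working it through.** There is no plan figure to reproduce. The check applies the three rules of SAP 6.11.1 literally to events that had already ended before the first dose.

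**Step 1. Worked cases.** First dose 15 March 2022.

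| What is known of the onset | AE from 3 to 10 March | AE from 20 February to 10 March |
|---|---|---|
| Full date | not TEAE | not TEAE |
| Month and year | **TEAE** | not TEAE |
| Year only | **TEAE** | **TEAE** |
| Nothing | not TEAE | not TEAE |

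Both events ended five days before dosing, so not TEAE is correct in every cell. The rule fails when the known month is the first-dose month, or when only the year is known and it is the first-dose year. It works when the known month is earlier than the first-dose month.

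**Step 2. How often the rule fails, given a pre-dose AE with a partial onset that has resolved.** This needs assumptions that are not in the documents. Let the onset fall k days before the first dose, with k uniform on 1 to 28, and let the first-dose day be uniform over a 30-day month. The onset falls in the first-dose month with probability (30 − k)/30.

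- All k from 1 to 28: mean k = 14.5, so (30 − 14.5)/30 = 0.517. Enumerating every first-dose day of 2022 gives 0.523.
- Resolution before dosing pushes onset earlier. If the event lasts at least 7 days, k runs from 8 to 28: mean k = 18, so 12/30 = 0.40.
- If it lasts at least 14 days, k runs from 15 to 28: mean k = 21.5, so 8.5/30 = 0.28.
- Year only, first dose uniform over 365 days, k from 1 to 28: 1 − 14.5/365 = 0.96.

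So about 28% to 52% of such events are misclassified when month and year are known, and about 96% when only the year is known.

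**Step 3. Illustrative count.** Suppose that 10% of the 320 subjects have one AE that resolved in screening, and that 5% to 20% of those AEs lack the onset day. Neither rate is in the documents.

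- Low: 320 × 0.10 × 0.05 × 0.28 = 0.4.
- High: 320 × 0.10 × 0.20 × 0.517 = 3.3.
- Extreme, if every incomplete date also lacked the month: 320 × 0.10 × 0.20 × 0.96 = 6.1.

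**Step 4. After the fix.** With the resolution-date exception extended to partial onset dates, every case in Step 1 and every enumerated date in Step 2 becomes not TEAE, so misclassification falls to 0%.

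**The case against.** The strongest reply is that this hardly matters. Onset dates must be documented (Protocol 5.7), a diary for health changes is handed out at Screening and reviewed at Baseline (Protocol 7.1, 7.2), and omissions in the eCRF must be explained (Protocol 12.3). A known stop date combined with an unknown onset day in so short a window should be rare. Such events precede dosing, so they should not differ systematically between arms. Over-counting TEAEs is the cautious direction, no inferential safety analysis is planned (Protocol 9.7), and the listings would show each case. All of that stands, and it limits the point to a minor one. It does not make the rule right.

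A second reply is that unknown start dates could be read to include partial ones. The text does not favour this, because it gives partial dates a separate sentence and a separate exception.

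A reader might also infer more than the documents support.

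- **That any resolved pre-dose AE with a known onset month is miscounted.** An earlier month is correctly excluded.
- **That the SAP charges placebo-period AEs with incomplete onset to AS012.** SAP 6.11.1 assigns AEs of re-randomised placebo subjects to a treatment, and TEAEs to Part I or later, by onset date. The readable text gives no default for incomplete dates. That is silence, not a stated rule that assigns them to AS012, and the public SAP has gaps, so a rule elsewhere cannot be ruled out.
- **That a specific number of false TEAEs can be predicted.** The counts above rest wholly on assumed rates.

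**Conclusion.** The point holds in a limited form. As written, the partial-date rule classifies an AE that ended before the first dose as treatment-emergent when its onset is known only to the first-dose month or only to the first-dose year. This contradicts the SAP's onset-based definition and the protocol's presence-based one, and nothing in the readable text repairs it. That conclusion follows from the wording alone.

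The size depends on assumptions about onset timing, event duration and the frequency of incomplete dates. On those used here it is probably a few events at most across five arms. No efficacy result is affected, and no bias between arms is expected. It is worth correcting because the rule is plainly wrong for these cases and the remedy is almost free.

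**What to change.** In the partial-date sentence of SAP 6.11.1, add a second ground for exclusion alongside the month-and-year one: the event is also not treatment-emergent if its resolution date falls before the study drug start date. This is the test that the preceding sentence already applies to unknown dates. An event whose resolution date is missing keeps its present classification.

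Optionally, and only for placebo subjects who were re-randomised to AS012, state the same test for attribution. An AE with incomplete onset that resolved before the first AS012 dose goes to Placebo, and one that resolved before the Week 24 visit goes to Part I. Do not add a general default that sends undecided events to AS012. It could charge an event to AS012 in a placebo subject who left before Week 24 and never took it.

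The main change costs one clause in the SAP and one condition in the TEAE derivation. The optional part adds a condition to each of two further derivations. Both are best made before the Week 24 unblinding, so that no date rule is settled with treatment known.
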